7.3 Analysis Visit Windows

Study days are calculated from the DBT Phase start date as follows:

- Measurement date – DBT Phase start date + 1, if measurement date \geq DBT Phase start date
- Measurement date – DBT Phase start date, if measurement date $<$ DBT Phase start date.

DBT days are calculated from the DB study drug start date as follows:

- Measurement date – DB study drug start date + 1, if measurement date \geq DB study drug start date
- Measurement date – DB study drug start date, if measurement date $<$ DB study drug start date.

OLE days are calculated from the OLE Phase start date as follows:

- Measurement date – OLE Phase start date + 1, if measurement date \geq OLE Phase start date
- Measurement date – OLE Phase start date, if measurement date $<$ OLE Phase start date.

OL rimegepant days are calculated from the OL rimegepant start date as follows:

- Measurement date – OL rimegepant start date + 1, if measurement date \geq OL rimegepant start date

- Measurement date – OL rimegepant start date, if measurement date < OL rimegepant start date.

Follow-up days are calculated from the OLE Phase last date as follows:

- Measurement date – OLE Phase last date + 1, if measurement date ≥ OLE Phase last date + 1
- Measurement date – OLE Phase last date, if measurement date < OLE Phase last date + 1.

General analysis visit windows (e.g. for safety parameters, MSQ, MIBS) are shown in Table 6.

Table 6 General Analysis Visit Windows

Analysis Period Analysis Visit	Abbreviation in Listings	Analysis Day Analysis Visit Window	Target Day
Screening Phase		Study Day	
Screening *		≤-1	
Baseline *		1	
Post-randomization @	Postrand	≥2	
DBT Phase		Study Day	
DBT EOT		≥2	
OLE Phase/OLE Outcomes Research		OLE Day	
Week 2		1 to 21	14
Week 4		22 to 42	28
Week 8		43 to 70	56
Week 12		71 to 98	84
Extension @	OLE Ext	≥99	
Follow-Up Phase			
Follow-Up Week 2	FU Week 2	1 to 21	14
Follow-Up Extension @	FU Ext	≥22	

* For subjects in the enrolled analysis set excluded from the full analysis set, the visit label is used for slotting.

@ Denotes an extended visit in the analysis period and is displayed only in listings

7.4 eDiary Data

The eDiary has the following question categories and key parameters which are used during the DBT and OLE Phases:

- Migraine question category:
 - Study medication parameters, from which the eDiary reported study medication date/time is derived (see Section 7.4.1.1)
 - Migraine characteristics parameters (see Section 7.4.2)

- Other medication taken to treat headache or aura status (yes or no).
- Headache (Non-migraine) question category: headache (nonmigraine) characteristics parameters (OLE Phase only; see Section 7.4.3)
- MQoL question category: MQoL question parameters at 24 hours postdose (see Section 7.4.4)
- Manual DCF Study medication question category: manual DCF study medication date (see Section 7.4.1.2).

A set of eDiary parameters is defined as those with the same eDiary finding date/time and eDiary completion date/time. The eDiary finding date/time is an internal date/time that is derived by YPrime after the subject answers the first question in the set. The eDiary completion date/time is an internal date/time that is derived by YPrime after the subject answers the last question in the set and saves the results.

Refer to the latest versions of the YPrime C4951004 Data Transfer Specification and eCOA System Requirements Document for additional details.

7.4.1 eDiary Study Medication

7.4.1.1 eDiary Reported Study Medication Date/time

The raw eDiary dataset has a reported study medication date/time parameter (DOSDATIM) with a value that is derived by YPrime from data entered by subjects in study medication parameters the Migraine question category. Date and time are both nonmissing.

Each distinct reported study medication date/time is derived from a distinct set of Migraine question category parameters at the time of prospective or retrospective study drug dosing.

A set of Migraine question category parameters at the time of prospective study drug dosing is defined as one in which (1) there is a “no” response to the eDiary question about already taking study medication, and (2) there is a “yes” response to the eDiary question about confirming that study medication was taken, and (3) eDiary planned time point is missing. The reported study medication date/time is derived by YPrime as the eDiary completion date/time.

A set of Migraine question category parameters at the time of retrospective study drug dosing is defined as one in which (1) there is a “yes” response to the eDiary question about already taking study medication, and (2) eDiary planned time point is missing. Subjects may enter study medication parameters retrospectively on or 1 day before the eDiary finding date as follows:

- During the DBT Phase, subjects must first report taking study medication either “today” or “other”.
 - If the response is “today”, then subjects must report the study medication time. The eDiary considers the date for “today” to be the same date as the corresponding eDiary finding date.

- If the response is “other”, then subjects must report both the study medication date and time.
- During the OLE Phase, subjects must report both the study medication date and time.

The reported study medication date/time is derived by YPrime from these subject-reported study medication parameter values, and seconds are set to “00”. Each distinct set of Migraine question category parameters at the time of study drug dosing is linked to a distinct eDiary reported study medication date/time as follows:

- A set of Migraine question category parameters at the time of retrospective study drug dosing is checked against eDiary reported study medication date/times. If the subject-reported study medication parameter values (with seconds of “00”) match the date/time components of a reported study medication date/time, then the set of Migraine question category parameters is considered linked to that “retrospective” eDiary reported study medication date/time.
- A set of Migraine question category parameters at the time of prospective study drug dosing is checked against reported study medication date/times that have not been already linked to Migraine question category parameters at the time of retrospective study drug dosing. If the eDiary completion date/time of the set of Migraine question category parameters matches an eDiary reported study medication date/time within ± 1 second, then the set of Migraine question category parameters is considered linked to that “prospective” eDiary reported study medication date/time.

For each reported study medication date/time record with distinct eDiary finding date/time, it is assumed that the subject took 1 tablet of study drug for that record.

The reported study medication date/time is used by the eDiary to collect (1) postdose data at 15 minutes through 48 minutes in the Migraine question category during the DBT Phase, and (2) MQoL data at 24 hours postdose in the MQoL question category during the DBT and OLE Phases.

7.4.1.2 eDiary Manual DCF Study Medication Date

The raw eDiary dataset has a manual DCF study medication date parameter (MDOSDAT) with a value that is entered by YPrime into the Manual DCF Study Medication question category. The data are provided from manual DCFs by sites on days subjects took study medication without using the eDiary.

For each manual DCF date record with distinct eDiary finding date/time, it is assumed that the subject took 1 tablet of study drug for that record.

The manual DCF medication date is not used by the eDiary to collect postdose data.

7.4.2 eDiary Migraine Characteristics

The following migraine characteristics parameters are collected in the Migraine question category (1) at the time of dosing during the DBT Phase and OLE Phases, and (2) at planned

time points postdose from 15 minutes through 48 hours (e.g., 15, 30, 45, 60, and 90 minutes; 2, 3, 4, 6, 8, 24 and 48 hours) during the DBT Phase for a single migraine attack:

- Migraine headache pain intensity (none, mild, moderate, severe)
- MBS (nausea, phonophobia, photophobia). Collected only before dosing (i.e., when there is a “no” response to the question about study medication already taken) during the DBT Phase.
- Nausea status (present, absent)
- Nausea intensity (mild, moderate, severe), if nausea status is present
- Phonophobia status (present, absent)
- Phonophobia intensity (mild, moderate, severe), if phonophobia status is present
- Photophobia status (present, absent)
- Photophobia intensity (mild, moderate, severe), if photophobia status is present
- Functional disability level (normal, mildly impaired, severely impaired, requires bedrest)
- Aura preceding or accompanying headache status (yes, no). Collected only at the time of dosing.

During the OLE Phase, the eDiary also collects migraine headache pain intensity regardless of study drug dosing.

Note that parameters collected “at the time of dosing” or without dosing in the Migraine question category have missing planned time point (see Section 7.4.1.1).

During the DBT Phase, the eDiary allows subjects to report 1 set of migraine characteristics parameters per planned time point.

- During the DBT Phase, the set of MQoL parameters is slotted into the 24-hour postdose analysis window using the difference between the reported DB study drug date/time and the eDiary finding date/time of the MQoL set (see [Sections 7.1 and 7.4.1.1](#)).

- During the OLE Phase, each distinct set of MQoL parameters is slotted into a 24-hour postdose analysis window using the difference between a reported OL rimegepant date/time and the eDiary finding date/time of the MQoL set (see Sections 7.1 and 7.4.1.1).

The eDiary collects MQoL data at 24 hours postdose in the MQoL question category only once during the DBT Phase, and up to 5 times during the OLE Phase.

Note that due to retrospective study drug dosing entry, subjects may have multiple sets of MQoL parameters in the same 24-hour postdose analysis window or on the same eDiary finding date during the OLE Phase.

Refer to the Core SAP for additional details about MQoL.

7.5 RM=F Algorithm

Efficacy measurements that are affected by the RM=F algorithm are migraine headache pain intensity, nausea status, photophobia status, phonophobia status, and functional disability level. Outcomes research measurements that are affected by the RM=F algorithm are MQoL Question 16, which is used to assess the reliability of rimegepant effect in the OLE Phase.

Let X denote a postdose time point: 15, 30, 45, 60, or 90 minutes; 2, 3, 4, 6, 8, 24, or 48 hours.

For a given measurement at time point X, the objective is to determine whether any rescue medication is taken at or before that measurement, even if the measurement is missing.

- For endpoints during the DBT Phase, the first DBT rescue medication date/time is compared to the reported DB study drug date/time and its corresponding postdose eDiary finding date/time for the measurement at time point X.
- For endpoints during the OLE Phase, all OLE rescue medication date/times are compared to each distinct reported OL rimegepant date/time and its corresponding postdose eDiary finding date/time for the measurement at time point X.

See Section 7.1 for the definitions of the reported DB study drug date/time, reported OL rimegepant date/time, and first DBT rescue medication date/time. See Section 6.2.6.3 for the definition of OLE rescue medications.

7.5.1 RM=F Algorithm During the DBT Phase

No DBT Rescue Medication Taken at or Before the Measurement in the X Analysis Window

No DBT rescue medication taken at or before the measurement in the X analysis window is defined as any of the following when the measurement is nonmissing in the X analysis window:

- No DBT rescue medication ever taken, i.e., missing first DBT rescue medication date (see Section 7.1)
- First DBT rescue medication date/time > {eDiary finding date/time for the measurement in the X analysis window}, if first DBT rescue medication time is not missing

- First DBT rescue medication date > {eDiary finding date for the measurement in the X analysis window}, if first DBT rescue medication time is missing.

DBT Rescue Medication Taken at or Before Time Point X (RM=F)

DBT rescue medication taken at or before time point X (RM=F) is defined as either (1) or (2):

- 1) DBT rescue medication taken at or before the measurement in the X analysis window. Defined as either of the following if the measurement is nonmissing in the X analysis window:
 - First DBT rescue medication date/time \leq {eDiary finding date/time for the measurement in the X analysis window}, if first DBT rescue medication time is not missing
 - First DBT rescue medication date \leq {eDiary finding date for the measurement in the X analysis window}, if first DBT rescue medication time is missing
- 2) DBT rescue medication taken at or before time point X and the measurement is missing in the X analysis window. Defined as either of the following:
 - (first DBT rescue medication date/time – reported DB study drug date/time) < upper bound of the X analysis window (see Table 7), if first DBT rescue medication time is not missing
 - First DBT rescue medication date \leq reported DB study drug date + Y days, if first DBT rescue medication time is missing
 - If X < 24 hours, then Y = 0.
 - If X = 24 hours, then Y = 1.
 - If X = 48 hours, then Y = 2.

Note that criterion (2) is used only in sensitivity analyses of the primary efficacy endpoint (see Section 6.3.2.2).

7.5.2 RM=F Algorithm During the OLE Phase

During the OLE Phase, subjects may have multiple reported OL rimegepant date/times and multiple OLE rescue medication date/times.

Let [reported OL rimegepant date/time, MQoL eDiary finding date/time] denote an interval, where the MQoL data have been slotted into a 24-hour postdose analysis window based on the reported OL rimegepant date/time and MQoL eDiary finding date/time (see Section 7.4.4).

No OLE Rescue Medication Taken at or Before the MQoL Measurement in the 24-Hour Postdose Analysis Window

No OLE rescue medication taken at or before the nonmissing MQoL measurement in the 24-hour postdose analysis window is defined as any of the following when the measurement is nonmissing in the 24-hour postdose analysis window:

- There does not exist any OLE rescue medication date/time such that reported OL rimegepant date/time < OLE rescue medication date/time ≤ MQoL eDiary finding date/time, if OLE rescue medication time is not missing.
- There does not exist any OLE rescue medication date such that reported OL rimegepant date ≤ OLE rescue medication date ≤ MQoL eDiary finding date, if OLE rescue medication time is missing.

OLE Rescue Medication Taken at or Before the MQoL Measurement in the 24-Hour Postdose Analysis Window (RM=F)

OLE rescue medication taken at or before the nonmissing MQoL measurement in the 24-hour postdose analysis window (RM=F) is defined as any of the following when the measurement is nonmissing in the 24-hour postdose analysis window:

- There exists ≥1 OLE rescue medication date/time such that reported OL rimegepant date/time < OLE rescue medication date/time ≤ MQoL eDiary finding date/time, if OLE rescue medication time is not missing.
- There exists ≥1 OLE rescue medication date such that reported OL rimegepant date ≤ OLE rescue medication date ≤ MQoL eDiary finding date, if OLE rescue medication time is missing.

7.6 Nonstudy Medication Types

See Section 7.1 for derived dates.

DBT Concomitant Medications

DBT concomitant medications are defined as nonstudy medications taken within 9 days after DB study drug dosing and before the first dose of OL rimegepant, i.e., those meeting any of the following criteria:

- DB study drug date ≤ imputed start or imputed end date ≤ minimum{DB study drug date + 9 days; OL rimegepant start date – 1 day}
- DB study drug date ≤ imputed start or imputed end date ≤ DB study drug date + 9 days, if OL rimegepant start date is missing
- Imputed start date ≤ DB study drug date ≤ minimum{DB study drug date + 9 days; OL rimegepant start date – 1 day} ≤ imputed end date
- Imputed start date ≤ DB study drug date ≤ DB study drug date + 9 days ≤ imputed end date, if OL rimegepant start date is missing.

The 9-day window is chosen to align with the on-DBT safety analysis period (see Section 7.2).

Post-DBT Pre-OL Rimegepant Medications

Post-DBT pre-OL rimegepant medications are defined as nonstudy medications taken after DB study drug dosing + 9 days and before the first dose of OL rimegepant, i.e., those meeting any of the following criteria:

- DB study drug date + 9 days < imputed start or imputed end date < OL rimegepant start date
- Imputed start date < DB study drug date + 9 days < OL rimegepant start date < imputed end date.

OL Rimegepant Concomitant Medications

OL rimegepant concomitant medications are defined as nonstudy medications taken from the first dose of OL rimegepant through the last dose of OL rimegepant + 9 days, i.e., those meeting any of the following criteria:

- OL rimegepant start date ≤ imputed start or imputed end date ≤ OL rimegepant last date + 9 days
- OL rimegepant start date ≤ imputed start or imputed end date, and OL rimegepant last date is missing
- Imputed start date ≤ OL rimegepant start date ≤ OL rimegepant last date + 9 days ≤ imputed end date
- Imputed start date ≤ OL rimegepant start date ≤ imputed end date, and OL rimegepant last date is missing.

The 9-day window is chosen to align with the on-OL rimegepant safety analysis period (see Section 7.2).

Follow-Up Medications

Follow-up medications are defined as nonstudy medications taken after study drug discontinuation + 9 days, i.e., study drug last date + 9 days < imputed start date or imputed end date.

7.7 IOL=F Algorithm During the OLE Phase

Outcomes research measurements that are affected by the IOL=F algorithm are MQoL Question 16, which is used to assess the reliability of rimegepant effect in the OLE Phase.

During the OLE Phase, subjects may have multiple reported OL rimegepant date/times and multiple manual DCF OL rimegepant dates (see Section 7.1).

Let [reported OL rimegepant date/time_i, MQoL eDiary finding date/time] denote an interval, where the MQoL data have been slotted into a 24-hour postdose analysis window based on the *i*th reported OL rimegepant date/time_i and MQoL eDiary finding date/time (see Section 7.4.4).

No Intervening OL Rimegepant Taken at or Before the MQoL Measurement in the 24-Hour Postdose Analysis Window

No intervening OL rimegepant taken at or before the MQoL measurement in the 24-hour postdose analysis window is defined as any of the following when the measurement is nonmissing in the 24-hour postdose analysis window:

- There does not exist any reported OL rimegepant date/time $_j$ such that reported OL rimegepant date/time $_i < \text{OL rimegepant date/time } _j \leq \text{MQoL eDiary finding date/time}$, where $i \neq j$.
- There does not exist any manual DCF OL rimegepant date such that reported OL rimegepant date $_i \leq \text{manual DCF OL rimegepant date} \leq \text{MQoL eDiary finding date}$.

Intervening OL Rimegepant Taken at or Before the MQoL Measurement in the 24-Hour Postdose Analysis Window (IOL=F)

Intervening OL rimegepant taken at or before the MQoL measurement in the 24-hour postdose analysis window (IOL=F) is defined as any of the following when the measurement is nonmissing in the 24-hour postdose analysis window:

- There exists ≥ 1 reported OL rimegepant date/time $_j$ such that reported OL rimegepant date/time $_i < \text{OL rimegepant date/time } _j \leq \text{MQoL eDiary finding date/time}$, where $i \neq j$.
- There exists ≥ 1 manual DCF OL rimegepant date such that reported OL rimegepant date $_i \leq \text{manual DCF OL rimegepant date} \leq \text{MQoL eDiary finding date}$.

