3.2.2.2 Other Secondary Objective Estimands

The estimands corresponding to the other secondary objectives are shown in Table 3.

Table 3 Other Secondary Objective Estimands

Objective 1	Reliability of rimegepant effect in the OLE Phase
Outcome Research Endpoint	Percentages of subjects achieving response after (1) the single evaluable qualifying migraine attack (EQMA) in the DBT Phase for those randomized to rimegepant, and (2) each of the first 5 EQMAs ≥ 23 hours apart in the OLE Phase. 
 Reliability of rimegepant effect during the OLE Phase is defined as proportions for ≥ 4 of the first 5 EQMAs ≥ 23 hours apart in the OLE Phase being no more than 7% less than the proportion in the DBT Phase. Response is defined as a category of “moderately better” or “very much better” for MQoL Question 16 (overall change in migraine symptoms since taking study medication) at 24 hours postdose. EQMAs are defined in Section 6.5.1.1.
Summary	Percentages of subjects achieving response after (1) the single EQMA in the DBT Phase for the DBT efficacy analysis set randomized to rimegepant, and (2) each of the first 5 EQMAs ≥ 23 hours apart in the OLE Phase in the OLE efficacy analysis set
Intercurrent Event	Rescue medication use: composite strategy Intervening OL rimegepant use: composite strategy Nonrescue acute headache medication use: treatment policy strategy Prophylactic migraine medication use: treatment policy strategy Study drug discontinuation: treatment policy strategy
Objective 2	Mean change from historical baseline in the number of migraine days per month by headache pain intensity (total; moderate or severe) in each month and over the entire OLE Phase
Efficacy Endpoint	Mean change from historical baseline in the number of migraine days per month by headache pain intensity (total; moderate or severe) in each month (defined as a 4-week interval), and over the entire OLE Phase (Weeks 1 to 12)
Summary	Change from historical baseline using descriptive statistics by treatment group and overall for the OLE migraine analysis set

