6.5.1.1 Reliability of Rimegepant Effect in the OLE Phase

Reliability of rimegepant effect in the OLE Phase is assessed using the proportions of subjects achieving response after (1) the single EQMA in the DBT Phase (i.e., π_{DBT}) for the DBT efficacy analysis set randomized to rimegepant, and (2) each of the first 5 EQMAs ≥ 23 hours apart in the OLE Phase (i.e., $\pi_{\text{OLE}i}$, $i = 1, \dots, 5$) for the OLE efficacy analysis set.

An EQMA is defined as a qualifying migraine attack (see Section 6.3.5.5) with a nonmissing MQoL Question 16 value at 24 hours postdose.

Reliability of rimegepant effect in the OLE Phase is defined as percentages for ≥ 4 of the first 5 EQMAs ≥ 23 hours apart in the OLE Phase being no more than 7% less than the percentage in the DBT Phase, i.e., $\pi_{\text{DBT}} - \pi_{\text{OLE}i} \leq 7\%$ for ≥ 4 of the 5 $\pi_{\text{OLE}i}$.

Response is defined as a category (value) of “moderately better” or “very much better” for MQoL Question 16 (overall change in migraine symptoms since taking study medication) at 24 hours postdose.

For a given EQMA, subjects who meet all the following criteria are classified as responders:

- MQoL Question 16 value of “moderately better” or “very much better” at 24 hours postdose, i.e., in the 24-hour postdose analysis window
- No rescue medication taken at or before the MQoL Question 16 value in the 24-hour postdose analysis window (see Section 7.5)

- **No intervening OL rimegepant taken at or before** the MQoL Question 16 value in the 24-hour postdose analysis window (see Section 7.7). This applies only to MQoLs in the OLE Phase.

For a given EQMA, subjects who are not responders are classified as failures. Failure criteria include any of the following:

- Rescue medication taken at or before the MQoL Question 16 value in the 24-hour postdose analysis window (RM=F; see Section 7.5)
- **Intervening OL rimegepant taken at or before** the MQoL Question 16 value in the 24-hour postdose analysis window (Intervening OL Rimegepant = Failure [IOL=F]; see Section 7.7). This applies only to MQoLs in the OLE Phase.
- MQoL Question 16 value of “A little better”, “No change”, “A little worse”, “Moderately worse” or “very much worse” at 24 hours postdose.

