Thus, for a given EQMA, subjects with missing MQoL Question 16 value at 24 hours postdose are excluded, i.e., missing MQoL Question 16 data are not imputed. For a given EQMA, the percentage is calculated against the number of evaluable subjects, i.e., those defined as responders or failures.

For the single EQMA in the DBT Phase, analyses are based on the DBT efficacy analysis set randomized to rimegepant with EQMA and MQoL eDiary measurement dates in the DBT Phase analysis period.

For the first 5 EQMAs ≥ 23 hours apart in the OLE Phase, analyses are based on the OLE efficacy analysis set with EQMA and MQoL eDiary measurement dates in the OLE outcomes research analysis period.

The RM=F algorithm (criterion 1 only) is applied to the single EQMA in the DBT Phase, and to the first 5 EQMAs ≥ 23 hours apart in the OLE Phase. For a given EQMA, subjects who take rescue medication at or before the MQoL measurement at 24 hours post dose are classified as failures.

The IOL=F algorithm is applied only to the first 5 EQMAs ≥ 23 hours apart in the OLE Phase. For a given EQMA, subjects who take intervening OL rimegepant at or before the MQoL measurement at 24 hours post dose are classified as failures.

See Section 9.3.1 for additional details.

Table of Reliability of Rimegepant Effect

The table of reliability of rimegepant effect displays the following for each EQMA by overall:

- Response rate (i.e., “n/N” and percentage; π_{DBT} , π_{OLEi} , $i = 1, \dots, 5$), ASE, and 95% CI. For a given EQMA, the percentage is calculated against the number of evaluable subjects (“N”), i.e., those defined as responders or failures.

- Percentage difference $\pi_{\text{DBT}} - \pi_{\text{OLE}i}$ for each EQMA in the OLE Phase. Percentage differences $<7\%$ are identified.

A footnote defines the reliability of rimegepant effect, and states whether it was achieved. CIs are based on the normal approximation to the binomial distribution.

Results support other secondary objective #1.

The table of reliability of rimegepant effect is also produced using the first 5 EQMAs ≥ 47 hours apart in the OLE Phase as a sensitivity analysis.

Frequency Table of MQoL Overall Change in Migraine Symptoms Outcomes by EQMA

The frequency table of MQoL overall change in migraine symptoms (Question 16) outcomes displays the number and percentage of subjects by treatment group/OL rimegepant and overall in the following categories and subcategories at each EQMA:

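### SAP 7.7 lets a re-dosed open-label attack meet both the no-intervening-dose definition and IOL=F, so it can pass the responder test that the failure rules say it fails

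*SAP*

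**What the plan says.** Other secondary objective 1 compares the percentage of responders after the single double-blind (DBT) attack on rimegepant with the percentage after each of the first five evaluable OLE attacks. Reliability is declared if the DBT percentage exceeds the OLE percentage by no more than 7 points for at least four of the five. A table footnote states whether it was achieved (SAP 6.5.1.1).

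Table 3 in SAP 3.2.2.2 treats rescue as part of the outcome ("Rescue medication use: composite strategy") and does the same for an intervening OLE dose. SAP 6.5.1.1 carries this out in two ways:

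- **Responder test.** All of three criteria are needed: a Question 16 answer in one of the two top improvement categories, no rescue by then (pointing to 7.5), and no intervening OLE dose by then (pointing to 7.7).
- **Failure rules.** "For a given EQMA, subjects who are not responders are classified as failures". Rescue and an intervening dose are each listed as failure criteria, and the section later repeats both as plain statements. Protocol 9.3.1 says the same of intervening doses.

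The definitions behind these rules are in SAP 7.7 and 7.5.2. In 7.7 the wording is "No intervening OL rimegepant taken at or before the MQoL measurement in the 24-hour postdose analysis window is defined as any of the following". One bullet covers eDiary-reported doses; the other begins "There does not exist any manual DCF OL rimegepant date such that reported OL rimegepant date". IOL=F is also an any-rule, and its matching bullet begins "There exists ≥ 1 manual DCF OL rimegepant date such that reported OL rimegepant date". In 7.5.2 the wording is "No OLE rescue medication taken at or before the nonmissing MQoL measurement in the 24-hour postdose analysis window is defined as any of the following", but there each bullet applies only if the rescue time is recorded, or only if it is missing.

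**The concern.** An intervening dose can come from either of two sources, so IOL=F is rightly an any-rule. Its opposite has to require that neither source shows a dose. SAP 7.7 instead accepts the absence of a dose in one source. A second dose reported in the eDiary, with no DCF entry, then satisfies the no-intervening-dose definition through the DCF bullet, and satisfies IOL=F through the reported-dose bullet.

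The responder test points to the faulty definition and is applied before the remainder are called failures. A programmer who codes it as written would count a re-dosed attack with a good Question 16 answer as a response, while another who codes the failure list would count it as a failure. The frequency table in 6.5.1.1 lists responders and IOL=F failures as separate categories, and this attack fits both. IOL=F applies only in the OLE, so any such error acts on the OLE percentages alone and makes the 7-point limit easier to meet.

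**Working it through.** **1. Truth table for SAP 7.7.** Let R = a reported intervening dose exists and D = a manual DCF intervening dose exists. As written, no intervening dose = (not R) or (not D); IOL=F = R or D. With *all*, no intervening dose = (not R) and (not D).

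| R | D | No dose, as written | No dose, with *all* | IOL=F |
|---|---|---|---|---|
| no | no | met | met | not met |
| no | yes | met | not met | met |
| yes | no | met | not met | met |
| yes | yes | not met | not met | met |

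As written, two of four rows meet both definitions. With *all*, the definitions are exact complements in all four rows.

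**2. The SAP's own example (9.3.1).** The 23-hour and 47-hour selection rules were re-applied to the five dose times and reproduce the printed inclusions: yes/no/yes/no/yes for the main analysis and yes/no/no/yes/no for the sensitivity analysis. The gaps after the first and third attacks are:

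- Attack 1 (01 Jan, 10:25) to attack 2 (02 Jan, 08:32): 22 h 07 min.
- Attack 3 (03 Jan, 08:35) to attack 4 (04 Jan, 06:22): 21 h 47 min.

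The 24-hour MQoL window opens after 23 hours (SAP Table 7), so both later doses precede the MQoL. Attacks 1 and 3 are both in the main analysis and both are IOL=F. If there is no DCF entry, both also meet the no-intervening-dose definition as written. The pattern is foreseeable because the OLE dosing limit in Protocol 4.1 is stated per calendar day. The 47-hour sensitivity analysis keeps attack 1 and uses the same definitions, so it does not test the problem.

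**3. SAP 7.5.2.** Read as cases, a single timed rescue record falls under the first bullet only and a single untimed record under the second only; each is classified correctly. The gap appears when a subject has both kinds of record, for example a timed rescue inside the interval and an untimed one outside it. The untimed no-rescue bullet then holds while the timed RM=F bullet also holds. Section 7.5.2 itself says that subjects may have several rescue records. The DBT algorithm in 7.5.1 tests only the first rescue record, so its cases cannot overlap in this way.

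**4. Effect on the 7-point limit.** Let g be the true DBT minus OLE gap and q the percentage points of evaluable OLE attacks wrongly passed as responses. The displayed gap is g − q. The documents do not give q; the values below are assumptions.

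| g (points) | q that brings the gap to 7 |
|---|---|
| 8 | 8 − 7 = 1 |
| 10 | 10 − 7 = 3 |
| 12 | 12 − 7 = 5 |
| 15 | 15 − 7 = 8 |

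**5. Attacks without Question 16.** SAP 6.5.1.1 says: "Thus, for a given EQMA, subjects with missing MQoL Question 16 value at 24 hours postdose are excluded". If a share m of attacks is rescued without an MQoL and the displayed rate is p, counting them as failures gives p(1 − m). With assumed m of 2% to 10% and p of 50% to 60%, the fall runs from 0.50 × 0.02 = 1 point to 0.60 × 0.10 = 6 points. The same exclusion applies to the DBT percentage, so the difference becomes p_DBT(1 − m_DBT) − p_OLE(1 − m_OLE). Whether that is larger or smaller than before depends on two unknown shares.

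**The case against.** The strongest reply is that the intent is not in doubt. The failure list in SAP 6.5.1.1, the two later statements in the same section, the composite strategy in 3.2 and Protocol 9.3.1 all make a re-dosed attack a failure, and the positive definitions of IOL=F and RM=F are correct. This stands. A reader might infer that rescue and re-dosing have ceased to count as failures in the OLE; the documents do not support that. They contradict themselves at one definition, and an attack is misclassified only if that definition is programmed literally and the failure rules are passed over.

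A reader might also treat 7.5.2 as the same error. It is narrower: its bullets are conditional on whether the time is recorded, and a timed rescue alone passes only if a bullet whose condition does not apply is counted as met.

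Finally, a reader might infer that dropping rescued attacks with no Question 16 answer turns failures into responses or biases the comparison. A dropped attack is neither. The exclusion is prespecified in Protocol 9.3.1.2 and SAP 6.5.1.1, SAP 3.2.2.2 gives its reason, and it applies in both phases. Counting such attacks as failures in the OLE only would create an asymmetry against reliability.

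What survives is the overlap in 7.7, which no reading of its two unconditional bullets removes.

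**Conclusion.** There is a real logic error in SAP 7.7 and a smaller gap in 7.5.2. Both lie in operative rules for an endpoint whose achievement will be declared. If coded literally they can only raise the OLE percentages, and so can only favour a finding of reliability. The size is unknown: it depends on how many evaluable attacks have an intervening dose, or mixed rescue records, together with a good Question 16 answer. The illustration of 1 to 8 points rests on assumed values and does not show that bias will occur.

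The reach is limited. The endpoint is an other secondary one, presented descriptively and outside the testing hierarchy. The reliability table is not among the outputs listed for the primary completion report in SAP 8.1. Primary and key secondary tests are untouched.

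**What to change.** - In SAP 7.7, have the no-intervening-dose definition require all of its bullets, or define it simply as not IOL=F.
- In SAP 7.5.2, do the same for the no-rescue definition, or define it as not RM=F, so that subjects with timed and untimed rescue records are classified once.
- Optionally, add a sensitivity analysis that counts rescued attacks with missing Question 16 as failures in both the DBT and the OLE percentages.

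The first two changes cost a word or a line each, need no new data, and bring the definitions into line with the SAP's own failure rules. SAP Section 7 allows conventions to be modified in dataset specifications, but this one decides responder status and is better corrected in the SAP itself, before the reliability outputs for the final report are programmed. The optional analysis costs some programming. SAP 6.3.5.5 already derives the first five qualifying OLE attacks regardless of MQoL, with rescue after each, and criterion 2 in 7.5.1 already covers DBT rescue with a missing measurement, although its stated use would have to be extended. The main analysis can keep the protocol's definition of an evaluable attack.
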